1.2 Exploratory Objectives

Clinical

1.2.1

To determine if caspofungin is associated with a lower incidence of proven/probable IFI during the first 100 days following high-risk allogeneic HCT compared with azole (fluconazole or voriconazole) prophylaxis.

1.2.2

To determine if caspofungin is associated with a lower incidence of proven/probable IFI during the first 42 and 100 days following high-risk allogeneic HCT compared with fluconazole prophylaxis.

1.2.3

To determine if caspofungin is associated with a lower incidence of proven/probable IFI during the first 42 and 100 days following high-risk allogeneic HCT compared with voriconazole prophylaxis.

1.2.4

To determine if caspofungin is associated with a superior fungal-free survival (FFS) (time to death or proven/probable IFI) at 42 and 100 days following high-risk allogeneic HCT compared with azole prophylaxis.

1.2.5

To describe the effect that caspofungin and azoles have on the incidence and severity of acute graft-versus-host disease (GVHD).

Biological

1.2.6

To define the test characteristics of weekly Fungitell Assay testing for identifying IFI in pediatric HSCT recipients receiving antifungal prophylaxis during the post-transplant neutropenic period.

1.2.7

To create a DNA specimen bank in anticipation of the development of biology correlative studies exploring the relationship between IFI and single nucleotide polymorphisms (SNPs) of genes involved in immunity.

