Assuming the incidence of IFI during the period at risk for the primary objective (Day 0 to Day 42) is 7% in the control patients (with fluconazole or voriconazole) and that the incidence of IFI is 2% with caspofungin prophylaxis, we will require 560 randomized patients (approximately 280 per arm) to achieve 80% power at 2-sided alpha level of 0.05. The power consideration is based on a 2-sample log rank test comparing the time to (first occurrence of proven/probable) IFI. Time to IFI is assumed to follow an exponential distribution. The observation period for the primary endpoint is from Day 0 till Day +42 following high-risk allogeneic HCT. Under an exponential time-to-IFI model with these parameters, the incidence of IFI is distributed almost evenly during the at-risk period; for each one-third of at-risk period (~14 days), the incidence of IFI is 2.3%-2.4% for patients on the azole arm and is 0.66%-0.67% for patients on the caspofungin arm. A 5% exponential loss-to-follow-up during the at-risk period is also included in the power consideration. Considering up to 5% of the enrolled patients might be deemed ineligible, the maximum enrollment number is adjusted to 590. The expected number of IFI among 280 eligible azole arm patients is 19.6.

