9.3.4 Analysis Plans

Descriptive Analyses

Standard descriptive statistics will be used to describe subjects' baseline characteristics and study outcome measures overall and within each treatment group. Summary statistics such as means, standard deviations, medians, and ranges will be produced for all measured variables. The balance of baseline measures across the treatment groups will be examined using appropriate two-sample tests.

Analysis for Primary Objective

For the primary endpoint, the at-risk period for IFI is from Day 0 until Day +42. Events that will shorten the at-risk IFI observation period (including death, withdrawal consent for data submission, or patient loss to follow-up) prior to Day +42 are expected to be rare. Since death (a true competing risk event) prior to Day +42 is expected to be rare, in the primary analysis all these events will be treated as censoring events and standard survival data methods will be performed. The primary analysis will be based on the principle of intention to treat (i.e., by the treatment assignment of patients at randomization, regardless of subsequent

compliance with the assigned treatment). All eligible and randomized patients with available IFI data will be included in this analysis. A modified intention to treat analysis which only includes patients who complied with the randomized treatment will also be performed as an exploratory analysis to evaluate whether its result differs from that of the intention to treat analysis. Kaplan-Meier curves will be used to estimate the time to onset of proven/probable IFI for patients randomized to the 2 arms. Log rank test will be used to compare the incidence of IFI between the 2 randomized arms during the at-risk period up to Day +42. The primary analyses will be performed at overall 2-sided alpha level of 0.05, with two planned interim efficacy analyses (see Section 9.3.5). Cox proportional hazards models will also be used to explore the treatment difference between the 2 arms on time to IFI with adjustment for covariates such as stratification factors or other potential risk factors.

Exploratory Analyses on Clinical Endpoints

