For exploratory objective 1, to examine the longer term treatment effect, a similar log rank test will be performed comparing the incidence of proven/probable IFI between the 2 randomization arms by extending the observation period up to Day +100. For exploratory objective 2 & 3, log rank test will be used to compare the incidence of proven/probable IFI of patients randomized to caspofungin within the particular randomization stratum defined by the comparator (fluconazole or voriconazole) to that of patients randomized to the comparator within the same stratum. For exploratory objective 4 on fungal-free-survival, failures for this endpoint will include death or proven/probable invasive fungal infection. Log rank test will be used to explore any treatment differences between the 2 arms on fungal-free-survival. For exploratory objectives 1-4, Cox proportional hazards models will also be used to examine the treatment difference between the 2 arms on time to IFI or fungal-free-survival with adjustment for other risk factors. For exploratory objective 5, the binary incidence of acute GVHD and the percentage distribution of acute GVHD by stage and by overall clinical grade will be estimated for each arm and compared between the 2 arms by Chi-square test. Logistic regression models (for the binary GVHD incidence data) or proportional odds models (for the ordinal GVHD data by stage or overall clinical grade) will also be used to explore the treatment difference between the 2 arms with adjustment for other risk factors such as donor HLA match score.

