Table 4 reviews the approach to assessing GVHD as acute, chronic, or the overlap between the two.

Finally, *engraftment syndrome* will be reported separately from the GVHD scoring presented below.

Engraftment Syndrome

A clinical syndrome of fever, rash, respiratory distress, and diarrhea has been described just prior to engraftment in patients undergoing unrelated cord blood and mismatched transplantation. If in the judgment of the local investigator a patient experiences this syndrome, details of the event should be reported when requested in the study CRFs.

Modified Glucksberg Staging Criteria for Acute Graft versus Host Disease

Table 1. Organ Staging (See tables and text below for details)

| Stage | Skin | Liver (bilirubin) | Gut (stool output/day) |
|----------|---|-------------------|---|
| 0 | No GVHD rash | < 2 mg/dL | Adult: < 500 mL/day Child: < 10 mL/kg/day |
| 1 | Maculopapular rash < 25% BSA | 2-3 mg/dL | Adult: 500-999 mL/day Child: 10-19.9 mL/kg/day Or persistent nausea, vomiting, or anorexia, with a positive upper GI biopsy. |
| 2 | Maculopapular rash 25% – 50% BSA | 3.1-6 mg/dL | Adult: 1000-1500 mL/day Child: 20-30 mL/kg/day |
| 3 | Maculopapular rash > 50% BSA | 6.1-15 mg/dL | Adult: >1500 mL/day Child: > 30 mL/kg/day |
| 4 | Generalized erythroderma plus bullous formation and desquamation > 5% BSA | >15 mg/dL | Severe abdominal pain with or without ileus, or grossly bloody stool (regardless of stool volume). |

For GI staging: The “adult” stool output values should be used for patients > 50 kg in weight. Use 3 day averages for GI staging based on stool output. If stool and urine are mixed, stool output is presumed to be 50% of total stool/urine mix.

For Stage 4 GI: the term “severe abdominal pain” will be defined as:

- (a) Pain control requiring institution of opioid use, or an increase in on-going opioid use, PLUS
- (b) Pain that significantly impacts performance status, as determined by the treating MD.

If colon or rectal biopsy is +, but stool output is < 500 mL/day (< 10 mL/kg/day), then consider as GI Stage 0.

There is no modification of liver staging for other causes of hyperbilirubinemia

Overall Clinical Grade (based on the highest stage obtained):

Grade 0: No Stage 1-4 of any organ

Grade I: Stage 1-2 skin and no liver or gut involvement

Grade II: Stage 3 skin, or Stage 1 liver involvement, or Stage 1 GI

Grade III: Stage 0-3 skin, with Stage 2-3 liver, or Stage 2-3 GI

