Grade IV: Stage 4 skin, liver or GI involvement

Table 2. Evaluating Liver GVHD in the Absence of Biopsy Confirmation

Establishing liver GVHD with no skin or GI GVHD

| | | |
|---------------------------------------|--|--|
| No Skin/GI GVHD Day 0-35 | Assume no liver GVHD unless proven by biopsy | |
| No Skin/GI GVHD Day 36-100 | If NO other etiology identified, NO improvement with stopping hepatotoxic medications/TPN: Stage as liver GVHD | If other etiology identified or improves with stopping hepatotoxic drugs/TPN: Do not stage as liver GVHD |

Establishing liver GVHD with skin or GI GVHD and other cause of hyperbilirubinemia

| | | |
|------------------------------------|---|---|
| Skin and/or GI GVHD present | Worsening bilirubin level (includes worsening just prior to onset of skin or GI tract GVHD) OR stable elevated bilirubin despite resolution of non-GVHD cause of increased bilirubin: Stage as liver GVHD | Stable or improving bilirubin after diagnosis of skin or GI GVHD, irrespective of treatment: Do not stage as liver GVHD |
|------------------------------------|---|---|

Changing liver GVHD stage with other cause of hyperbilirubinemia

| | |
|--|--|
| Skin and GI GVHD stable, improving, or absent | Liver GVHD staging is carried forward without increase in stage until other disease process resolves (e.g., if TTP is diagnosed in the presence of Stage 2 liver GVHD, the liver GVHD Stage 2 is carried forward despite rising bilirubin level until TTP is resolved. If there is no liver GVHD – Stage 0 – and new onset TTP, the Stage 0 is carried forward until TTP is resolved). |
|--|--|

| | |
|---|---|

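### Acute GVHD stage and grade are ordered, but the one unadjusted comparison named for them is a chi-square test that ignores the order; an ordered test should carry the severity comparison

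*Combined protocol and SAP*

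**What the plan says.** Objective 1.2.5 is exploratory and reads "To describe the effect that caspofungin and azoles have on the incidence and severity of acute graft-versus-host disease (GVHD"). For this objective, Section 9.3.4 (Exploratory Analyses on Clinical Endpoints) plans two layers of analysis.

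- **Unadjusted.** Binary incidence is compared between arms; in addition, "the percentage distribution of acute GVHD by stage and by overall clinical grade will be estimated for each arm and compared between the 2 arms". Chi-square is the test named for both.
- **Adjusted.** Logistic models for incidence are planned, and "proportional odds models (for the ordinal GVHD data by stage or overall clinical grade) will also be used to explore the treatment difference". These models adjust for other risk factors, with donor HLA match score given as an example.

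Appendix III defines overall clinical grade on five levels, from "Grade 0: No Stage 1-4 of any organ" up to "Grade IV: Stage 4 skin, liver or GI involvement". Organ stage runs from 0 to 4.

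No significance level, power, effect size or expected grade distribution is stated for GVHD. The section does not say which of the two severity analyses carries the conclusion.

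**The concern.** A Pearson chi-square on a 2 x 5 table gives the same P-value however the five columns are arranged. It spends 4 degrees of freedom on any difference in mix and reports neither direction nor size. It suits incidence, which is binary, but not severity, which is the ordered half of the objective.

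For objectives 1 to 4 the same section names an unadjusted test (log rank) and then an adjusted model (Cox). In objective 5 the place of the log rank test is taken, for severity, by a test that discards the order.

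Two things are at stake. A real, consistent shift towards milder or worse GVHD could be missed by the unadjusted comparison although an ordered test on the same data would find it. The two planned analyses could also disagree about severity, with no rule set in advance for which one to report as the main result.

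**Working it through.** **Inputs from the documents.** Five ordered grades (Appendix III). About 280 patients per arm, from "560 randomized patients (approximately 280 per arm) to achieve 80% power at 2-sided alpha level of 0.05" (Section 9.3.3). A two-sided 0.05 level, which the plan states only for the primary analysis ("The primary analyses will be performed at overall 2-sided alpha level of 0.05") and which is assumed here for GVHD.

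**Inputs assumed.** All grade distributions and odds ratios below are assumptions.

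**Step 1: the plan's own figure.** There is no GVHD figure to reproduce. The primary power was recomputed as a check on the sample size:

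- HR = ln(0.98)/ln(0.93) = 0.278.
- With 5% exponential loss, 24.6 events are expected in 2 x 280 patients.
- Freedman's formula: z = sqrt(24.57) x (1 - 0.278)/(1 + 0.278) - 1.96 = 0.84, so power is 79.9%. This matches the stated 80%.

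**Step 2: cost of the extra degrees of freedom.** Suppose a two-sided 1-df ordered test has power p. Its noncentrality is about (1.96 + z_p)^2. The power of the 4-df chi-square at the same noncentrality is P(noncentral chi-square, 4 df > 9.488). For p = 80%, (1.960 + 0.842)^2 = 7.85, and the 4-df power is 59.5%.

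| Ordered test, 1 df | Chi-square, 4 df | Loss (points) |
|---|---|---|
| 50% | 30.8% | 19.2 |
| 60% | 38.9% | 21.1 |
| 70% | 48.2% | 21.8 |
| 80% | 59.5% | 20.5 |
| 90% | 74.0% | 16.0 |
| 95% | 83.7% | 11.3 |

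**Step 3: simulation.** Each scenario had 20,000 trials with 280 per arm, comparing the Pearson chi-square with the tie-corrected Wilcoxon. The second arm was formed by multiplying every cumulative odds by a common odds ratio. For example, a 50% share in grade 0 with OR 1.5 becomes 1.5/2.5 = 60.0%. Results for an assumed base of 50/20/15/10/5% in grades 0 to IV (losses taken before rounding):

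| OR | Wilcoxon | Chi-square | Loss (points) |
|---|---|---|---|
| 1.3 | 37.4% | 21.9% | 15.5 |
| 1.4 | 55.0% | 35.0% | 20.0 |
| 1.5 | 71.5% | 48.6% | 22.9 |
| 1.6 | 82.8% | 63.0% | 19.8 |
| 1.8 | 94.5% | 82.9% | 11.7 |
| 2.0 | 98.7% | 93.5% | 5.2 |
| 2.3 | 99.9% | 98.9% | 1.0 |

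Three other assumed bases were run: 40/20/20/13/7, 60/15/13/8/4 and 70/12/10/5/3%. Over all four bases the loss is 18 to 23 points wherever the ordered test has about 50-85% power. At OR 2.3 it is 0.4 to 6.1 points.

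**Step 4: type I error.** With identical distributions in both arms, chi-square rejects in 4.8-5.0% of trials and the Wilcoxon in 5.0-5.1%. Both hold their level.

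**Step 5: a different mix without a net shift.** Compare 50/20/15/10/5% with 45.1/30.0/15.0/6.9/2.9%, built so that a patient from either arm is equally likely to have the worse grade. Chi-square rejects in 69% of trials and the Wilcoxon in 5%. The distributions do differ here, so the chi-square rejection is correct, but it does not answer a question about severity.

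**The case against.** The strongest reply is that the plan already uses the ordering. The sentence after the chi-square plans a proportional odds model for these data and calls them ordinal. The objective is exploratory and worded as descriptive, with no power claim to lose. An omnibus test paired with an ordinal model is a defensible way to describe a distribution.

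Much of this stands:

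- A reader might infer that the plan ignores the order of the grades altogether. It does not. The power loss applies to the chi-square comparison, not to everything planned for objective 5.
- A reader might take Step 5 to mean that chi-square gives false positives. It does not. The plan says it compares the percentage distribution, a real difference in distribution is detected, and the level is held when there is none.
- A reader might take 20 points as this trial's loss. The documents contain nothing from which to derive that. The figure depends on the assumed distribution and shift.

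What the reply does not remove is that the ordinal model is an additional analysis and is adjusted for covariates that are not fully listed. No unadjusted ordered comparison is named, and nothing says which analysis carries the severity conclusion.

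**Conclusion.** The point holds as a minor improvement to the analysis. The unadjusted comparison named for GVHD stage and grade ignores the ordering. For a consistent shift it has less power than an ordered test on the same data: about 20 points less (at most 23 in the cases run) when the ordered test has roughly 50-85% power, and close to nothing for large shifts.

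This rests on 280 per arm, a two-sided 0.05 level, a proportional odds shift and assumed grade distributions. It has no bearing on the primary endpoint, the sample size or the interim rules.

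**What to change.** In Section 9.3.4, for exploratory objective 5:

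1. Keep chi-square for the binary incidence of acute GVHD.
2. For stage and overall grade, compare the arms by an ordered test, either the Wilcoxon rank-sum test or a proportional odds model with treatment as the only term. Report the common odds ratio with its 95% CI, and name this as the main severity comparison.
3. Keep the already planned covariate-adjusted proportional odds model as supportive, and keep the percentage distributions as tables.
4. If stratification by the randomization factors is wanted (2 x 2 x 3 = 12 strata), specify a stratified Wilcoxon (van Elteren) test. It is not equivalent to the unadjusted proportional odds score test, and the simulations above were unstratified, so they do not describe its power.

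The cost is a sentence or two of wording and no new data. The downside is lower power for differences in mix that do not follow the severity order, as in Step 5. The tabulated percentages would still show these.

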Based on the survey we performed, we expect about half of the enrolled patients will use fluconazole as the comparator and the other half will use voriconazole as the comparator. For the exploratory objective on comparing the incidence of IFI during the first 42 days between caspofungin and fluconazole or between caspofungin and voriconazole, with 140 patients per arm, the power to detect a difference in IFI incidence of 7% (comparator) vs. 2% (caspofungin) will be only about 51%. The power for a difference in IFI incidence of 7% (comparator) vs. 1% (caspofungin), 8% (comparator) vs. 2% (caspofungin), and 9% (comparator) vs. 2% (caspofungin) are 71%, 62%, and 71% respectively. These power considerations follow the same assumptions as those for the primary objective. For the exploratory objective on comparing the incidence of IFI during the first 100 days following high risk allogeneic HCT using the entire study population, assuming IFI incidence of 12% (with fluconazole or voriconazole) vs. 5% (caspofungin), the power to detect the difference is 81%. The incidence of IFI during this longer at-risk-period might be bimodal with the main peak during neutropenic period immediately after HCT; however due to lack of good estimate for such bimodal distribution, this power consideration is still based on exponential models and the incidence is distributed roughly evenly under these incidence assumptions. The power consideration for IFI up to Day 100 also includes a 15% exponential loss-to-follow-up. When only comparing patients randomized between caspofungin and one comparator (fluconazole or voriconazole), again with about half of the sample size (about 140 per arm), the power to detect IFI incidence during the first 100 days of 12% (comparator) vs. 5% (caspofungin) is only 52%. The power will be about 78% if the IFI incidence during the first 100 days is 14% (comparator) vs. 3% (caspofungin).

Analysis of beta-D Glucan Assay

Sensitivity, specificity, positive predictive value, and negative predictive value of the beta-D glucan assay will be determined using standard formulas and EORTC/MSG criteria as the gold standard. Please see Section 13.9 for additional statistical considerations for this aim.

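### The 78% power given for the single-comparator Day-100 comparison at 14% vs 3% does not follow from the plan's assumptions, which give about 88%

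*Combined protocol and SAP*

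**What the plan says.** Section 9.3.3 sets the basis for the power figures. It asks for "560 randomized patients (approximately 280 per arm) to achieve 80% power at 2-sided alpha level of 0.05". It adds that "The power consideration is based on a 2-sample log rank test comparing the time to (first occurrence of proven/probable) IFI" and that "Time to IFI is assumed to follow an exponential distribution". For the 42-day window, "A 5% exponential loss-to-follow-up during the at-risk period is also included in the power consideration".

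Section 9.3.4 (Exploratory Analyses on Clinical Endpoints) extends this to Day 100. It keeps exponential event times: "this power consideration is still based on exponential models and the incidence is distributed roughly evenly under these incidence assumptions". It changes the loss assumption: "The power consideration for IFI up to Day 100 also includes a 15% exponential loss-to-follow-up". For a comparison with a single azole it works "again with about half of the sample size (about 140 per arm"). Two Day-100 powers follow for that comparison: 52% for 12% vs 5%, and then "The power will be about 78% if the IFI incidence during the first 100 days is 14% (comparator) vs. 3% (caspofungin".

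No other test, alpha, sample size or loss rate is given for this last figure.

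**The concern.** The two Day-100 single-comparator figures share the same sample size, window, test and loss assumption, so one calculation should produce both. It produces 52% for 12% vs 5% but not 78% for 14% vs 3%.

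At stake is the description of what objectives 1.2.2 and 1.2.3 can detect by Day 100. The 14% vs 3% case is the only scenario offered for that comparison besides the 52% one. As printed, the sentence either understates the power at those rates or attaches 78% to a larger effect than the one that has it.

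**Working it through.** **Inputs.** Two-sided alpha 0.05, log-rank test, exponential event times (Section 9.3.3). Loss is exponential: 5% over 42 days (Section 9.3.3) and 15% over 100 days (Section 9.3.4). There are 280 per arm overall and 140 per arm for one comparator. Section 9.3.4 does not restate alpha for the Day-100 figures; 0.05 is carried over from Section 9.3.3.

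**Formulas.** Take the window as one time unit. For cumulative incidence p and loss L:

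- event hazard h = −ln(1 − p); loss hazard g = −ln(1 − L)
- probability of an observed event: e = h/(h + g) × [1 − exp(−(h + g))]
- expected events: d = n(e₁ + e₂); hazard ratio HR = h₂/h₁
- Freedman: power = Φ(√d × (1 − HR)/(1 + HR) − 1.96)
- Lachin-Foulkes, pooled under the null: power = Φ([√n |h₁ − h₂| − 1.96√V₀]/√V₁), where V₀ = 2h̄²/ē, V₁ = h₁²/e₁ + h₂²/e₂, h̄ is the mean of the two hazards and ē is e evaluated at h̄

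**Step 1: reproduce the plan's other figures.**

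| Window, n per arm, rates | Stated | Freedman | Lachin-Foulkes |
|---|---|---|---|
| Day 42, 280, 7% vs 2% | 80% | 79.9% | 80.1% |
| Day 42, 140, 7% vs 2% | 51% | 50.7% | 51.0% |
| Day 42, 140, 7% vs 1% | 71% | 70.6% | 70.9% |
| Day 42, 140, 8% vs 2% | 62% | 61.5% | 61.9% |
| Day 42, 140, 9% vs 2% | 71% | 70.8% | 71.2% |
| Day 100, 280, 12% vs 5% | 81% | 80.9% | 81.1% |
| Day 100, 140, 12% vs 5% | 52% | 51.8% | 52.1% |
| **Day 100, 140, 14% vs 3%** | **78%** | **87.6%** | **88.0%** |

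All seven comparison figures match to the whole percent by Lachin-Foulkes, and to within about half a point by Freedman. This identifies the method closely and supports alpha 0.05 for the Day-100 cases.

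**Step 2: the disputed case in full.**

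- h₁ = −ln 0.86 = 0.1508; h₂ = −ln 0.97 = 0.0305; g = −ln 0.85 = 0.1625
- e₁ = 0.1295 and e₂ = 0.0277, so expected events are 140 × e₁ = 18.13 and 140 × e₂ = 3.88; d = 22.0
- HR = 0.0305/0.1508 = 0.202
- Freedman: √22.0 × 0.798/1.202 = 3.115; 3.115 − 1.96 = 1.155; Φ = 87.6%
- Lachin-Foulkes: √140 × 0.1203 = 1.424; V₀ = 0.2052 and V₁ = 0.2092; (1.424 − 1.96 × 0.4530)/0.4574 = 1.172; Φ = 88.0%

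The 12% vs 5% case also has 22.0 expected events (15.53 + 6.47), but with HR 0.401. The two scenarios therefore differ only in hazard ratio, and moving from 0.40 to 0.20 raises power from 52% to 88%.

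**Step 3: could another method give 78%?** For 14% vs 3% with the stated n, alpha and loss:

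- Schoenfeld: 96.3%
- simulated log-rank: 91.8%
- two proportions: 91.4%, or 86.5% with n cut by 15%
- two proportions, continuity-corrected: 87.5%, or 80.7% with n cut by 15%
- Wald test on the log hazard ratio: 81.6%

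The two lowest, 80.7% and 81.6%, are still above 78%. They also miss the primary 80%, giving 73.1% and 75.0% there, so neither is the plan's method.

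**Step 4: what would give 78%?** By Lachin-Foulkes at 14% vs 3%, it would take about 106 per arm (77.9%) instead of 140, or loss above 50% (79.3% at 50%) instead of 15%. Alternatively, alpha would have to be roughly 0.02 (79.1%) instead of 0.05. At 140 per arm with 15% loss, nearby rate pairs come close: 12% vs 3% gives 77.8% and 14% vs 4% gives 79.5%.

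**The case against.** The best objection concerns weight. Objectives 1.2.2 and 1.2.3 are exploratory. The figure does not set the 560 eligible or 590 maximum enrolment, the alpha or the interim rules, and the within-stratum log-rank test is run the same way whatever power is printed. At the printed rates the error understates power, so it does not oversell the trial, and the adjacent 52% already warns that these comparisons are weak. All of this stands and limits the priority of the point. It does not make the sentence right.

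A second objection is that the plan names no power formula or software, so the method is inferred, and simulation of the log-rank test itself gives 91.8% rather than 88%. That is fair: 88% is the value on the plan's apparent approximation. But seven matches make the inference strong, and the simulated value lies further from 78%.

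A third is that several rate pairs give about 78%, and the documents do not show which was meant. This also stands. 12% vs 3% is a plausible source, not an established one.

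**Conclusion.** The concern holds. On the plan's stated assumptions the power for 14% vs 3% with 140 per arm is about 88% (87.6% to 88.0%), not 78%, a gap of about 10 points. None of the variants tried gives 78% with the stated inputs. Nothing elsewhere in the document corrects or explains the figure.

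The conclusion rests on carrying two-sided alpha 0.05 over from Section 9.3.3 and on reading the 15% loss as exponential over the 100-day window. Both are supported by the 52% and 81% figures, which reproduce on the same basis. Whether the power or a rate is the misprint cannot be settled from the document. The consequence is confined to one exploratory power statement.

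**What to change.** The sponsor's statistician should rerun this one case and correct whichever value is wrong. If 14% vs 3% was intended, state the power as about 88%. If 78% was the computed result, replace the rates with the pair that was actually run; 12% vs 3% is a candidate, at 77.8%. Naming the power formula or software in Section 9.3.3 would let a reader check all eight figures. The cost is one corrected sentence at the next amendment, with no effect on sample size, conduct or analysis.
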